The study will include IVF or ICSI stimulation cycles and the FET cycles linked to the same stimulation cycles among women who received rhFSH-alfa reference product, HP-hMG or rhFSH-alfa biosimilar products for COS (Figure 1). The overall qualifying event for study inclusion will thus be a recorded IVF/ICSI stimulation cycle with one of the study drugs. Three study cohorts will be created, including stimulation cycles with rhFSH-alfa reference product, HP-hMG, and rhFSH-alfa biosimilar products, respectively. Women may contribute cycles to more than one study cohort. Any linked FET cycles will be assigned to the same cohort as the stimulation cycle it originated from. The study will be restricted to the first five stimulation cycles observed in each woman in the IVF registers, regardless if they occurred in the study period and the gonadotropin (study drug or non-study drug) used for COS. The study is restricted to the first five stimulation cycles as it is known that the CLBR per cycle decreases over the first five cycles and is maintained at a similarly low level beyond the fifth stimulation cycle and the number of women continuing treatment diminishes substantially with each advancing cycle number (20,21). Further, the study population will be restricted to women who, on the day of treatment initiation (ovarian stimulation start) and 3 years prior, resided in the country where the treatment was performed. This will allow for a minimum baseline period of 3 years during which any previous IVF/ICSI treatment and information on potential confounders can be assessed.

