9.2 Setting

9.2.1 Study Population

This study will comprise IVF/ICSI stimulation cycles and FET cycles linked to the same stimulation cycles among women who received rhFSH-alfa reference product, HP-hMG or rhFSH-alfa biosimilar products for COS. The countries of study are Denmark and Sweden. The study population will be identified using registers with comprehensive nationwide coverage. Hence, all eligible IVF/ICSI cycles among the entire female population in each country will be included and the results from the study are expected to be representative of that population.

Women aged 18 years or more at ovarian stimulation start during the study period will be identified as eligible for inclusion in the study from each country's IVF Register. Individual-level data will then be linked to the Prescribed Drug Register, the National Patient Register, and the Medical Birth Register to further determine eligibility and ascertain baseline characteristics and safety and pregnancy outcomes. More details on each register are provided in Section 9.4.

For inclusion, all stimulation cycles will be assessed on a set of inclusion and exclusion criteria. The overall study population will include all women with at least one IVF/ICSI stimulation cycle fulfilling all eligibility criteria. Analysis-specific selection criteria, depending on the outcome of interest, will also be applied (see Section 9.7.1).

For inclusion of a stimulation cycle in the study, women must fulfill all of the following inclusion criteria:

1. *Initiated IVF/ICSI stimulation cycle with rhFSH-alfa reference product, HP-hMG or rhFSH-alfa biosimilar product monotherapy for COS during the study period²*
2. *Aged 18 years or more at stimulation cycle index date*
3. *Female sex at stimulation cycle index date*

Stimulation cycles are not eligible for this study if any of the following exclusion criteria are fulfilled:

1. *History of 5 or more IVF/ICSI stimulation cycles prior to the stimulation cycle index date*
2. *Ovarian stimulation for the purpose of oocyte donation, oocyte storage, embryo donation, oncological or other medically indicated embryo storage³, or preimplantation genetic testing (PGT)*
3. *Non-availability of individual-level data on IVF/ICSI treatment, dispensed drugs and medical history for 36 months or more prior to and including the stimulation cycle index*

² For Sweden, inclusion of eligible women may be limited to 31 December 2019 because of Q-IVF data availability.

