9.2.3 Study Time Periods

The overall **study period** is from 2010 through 2020. Different start dates are defined based on which two drugs are compared and, for the comparison with rhFSH-alfa biosimilar products, which country is analyzed. The study period ends on 31 December 2020 (or last available data) for both study drug comparisons and countries. Homogeneity in patient management over time, market entry of the comparator drugs and register lag times determine the start and end dates of the study period:

- rhFSH-alfa reference product vs. HP-hMG:
 - o Denmark, Sweden: 1 January 2010 – 31 December 2020
- rhFSH-alfa reference product vs. rhFSH-alfa biosimilar products:
 - o Denmark: 26 March 2014 – 31 December 2020
 - o Sweden: 20 June 2014 – 31 December 2020

For Sweden, inclusion of eligible women may need to be restricted to 31 December 2019, considering study timelines (see Section 6) and the typical two-year lag time for data availability from the Swedish National Quality Registry of Assisted Reproduction (Q-IVF) (see Section 9.4.2).

The overall **index date** is the date when the woman's *first* eligible IVF/ICSI stimulation cycle started (defined as start of ovarian stimulation) in the study period. The **stimulation cycle index date** is the date when each stimulation cycle started. For FET cycles linked to an included stimulation cycle, the cycle start date is the Last Menstrual Period (LMP) date for natural FET cycles or the date hormonal stimulation (replacement) treatment was started for stimulated FET cycles, as recorded in each country's IVF register.

The **baseline period** is defined as the 36-month minimum period prior to and including the (stimulation cycle) index date. During this period, (cycle) eligibility will be determined, and baseline covariates assessed. The baseline period may include time before the age of 18 years, for women who had IVF/ICSI treatment specifically at the age of 18 years. All available data from the registers will be used to obtain information on important covariates. Baseline data from the national patient registers, however, will be limited to the period in which ICD-10 coding has been

used comprehensively in each country (starting from 1994 in Denmark and 1998 in Sweden). The exact length of the baseline period will therefore vary between cycles within the same patient.

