9.7.1 Analysis Sets

To address the study objectives, analysis sets will be constructed based on the study outcomes as defined in Section 9.1.2. To allow for a sufficient time period to assess the outcomes after the initiation of a stimulation cycle, the analysis sets will be restricted to outcome-specific time periods. For the analysis sets, the following outcome-specific time periods are applied: 1 year after the stimulation cycle initiation for LBR, CPR, OPR, MC-CLBR and TTLB; 1 year after the stimulation cycle and linked FET initiation for CLBR, CCPR, COPR, pregnancy loss, multiple pregnancy and treatment-associated costs; 1.5 months after the stimulation cycle initiation for oocyte retrieval and embryos cryopreserved per initiated stimulation cycle, and cycle cancellation; 1 month after the stimulation cycle aspiration for oocyte retrieval and embryos cryopreserved per aspirated stimulation cycle; 4 months after stimulation cycle initiation for OHSS; 3 months after last embryo transfer for implantation. Fresh and frozen embryo transfers will be assessed by using all fresh and frozen embryo transfers done by the end of the study period (31 December 2020).

The analysis sets and their use for the study objectives and outcomes are defined in Table 5. The use of analysis sets will be described in the statistical analysis, and any needed specific modifications or restrictions on the analysis sets needed for the analysis of the study objectives will be further described in the SAP.

Table 5. Description of analysis sets

Analysis set	Description of the analysis set	Study objective(s)	Study outcome measure(s)
Set 1	Stimulation cycles with drug of interest initiated on or before 31 December 2019	Primary objective	LBR
		Secondary objective 1	CPR
			OPR
Set 2	Stimulation cycles with drug of interest and linked FET cycles initiated on or before 31 December 2019	Primary objective	CLBR
		Secondary objective 1	CCPR
			COPR
		Secondary objective 5	Pregnancy loss
		Secondary objective 6	Multiple pregnancy
Secondary objective 9	Treatment-associated costs		
Set 3	Stimulation cycles with drug of interest initiated on or before 15 November 2020 ⁺	Secondary objective 2	Oocytes retrieved per initiated stimulation cycle
			Embryos cryopreserved per initiated stimulation cycle
			Utilizable embryos per initiated stimulation cycle
		Secondary objective 7	Cycle cancellation

Analysis set	Description of the analysis set	Study objective(s)	Study outcome measure(s)

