3	Minimum duration of follow-up for assessment of MC-CLBR and TTLB	The main analyses of the MC-CLBR and TTLB each uses a minimum of 1 year of follow-up and includes women who had initiated their first-ever stimulation	1 year is considered sufficient to achieve at least one live birth and a reasonable number of complete cycles for reliable estimates of the MC-CLBR in view of previous studies considering up to 9 (20) and 8 (21) stimulation cycles for the estimation of cumulative live birth rates with at least 1.5 and 2 years of follow-up, respectively.	Minimum follow-up period extended to 2 years, thus restricting the analysis to women who had initiated their first-ever stimulation cycle on or before 31 December 2018.	The effect of extending the minimum follow-up period on the conservative and optimal estimates of the MC-CLBR and on TTLB will be explored. The analysis of each outcome will otherwise be repeated as described in 9.7.3.3 and 9.7.3.4.

No.	Topic	Main analysis		Sensitivity analysis	
		Method	Justification	Alteration to method	Justification
		cycle on or before 31 December 2019.			
4	CLBR	The main analysis does not consider the possible impact of oocyte yield on CLBR.	Oocyte yield is not considered in the stratified analysis.	CLBR in the first, second and third stimulation cycle will be estimated by the number of oocytes retrieved in the first cycle (cycle rank expressed as observed in the study period).	Oocyte yield is known to be positively associated with CLBR (20,40,41). The effect of oocyte yield in the first cycle will be explored for the CLBR. Otherwise the analysis will be repeated as described in 9.7.3.3 and 9.7.3.4, although rates will only be reported for the IPTW-weighted cohorts.

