the Danish National Board of Health suspected that were to some degree an under ascertainment of the true number of treatments initiated due to incomplete capture, noting that the use of electronic capture in future updates would improve quality (55,56). However, as only electronic reports are included during the period under study (2010-2020), previously identified limitations related to underreporting would not be an issue in this study. All treatment cycles and measurements on pregnancies from private and public IVF clinics are required to be reported, and the DIVF during the study period is based on electronic capture and complete and validated data (52). Similar to the Q-IVF, the DIVF has been used extensively in research (27,40,54,57,58).

As in any study assessing cumulative live birth rates of IVF treatment, uncertainty remains around end outcomes in those who discontinued treatment, had they continued. This uncertainty will be addressed by the estimation of conservative estimates and, in a sensitivity analysis, optimal estimates for the primary objective MC-CLBR outcome, based on different assumptions of live birth rates in women who discontinued treatment (see Analysis 2 in Table 8). Similarly, the impact on the conservative and optimal MC-CLBR estimates of extending the minimum follow-up to 2 years will also be explored (see Analysis 3 in Table 8).

Further, prescribing patterns of the study drugs are likely to vary to some extent across the study period. If one drug was favored over the other in the early part of the study period, the probability of observing all live births in up to five stimulation cycles using that drug would be higher than for the other one (due to availability of data with longer follow-up). Based on the feasibility assessment of the use of the study drugs in Denmark and Sweden, it is known that the use of rhFSH-alfa biosimilar products has increased gradually, with a relatively larger proportion observed during the latter part of the study period, compared with rhFSH-alfa reference product (37). Hence, it cannot be ruled out that this may lead to a downward bias for the cumulative live birth rate outcomes following COS with rhFSH-alfa biosimilar products.

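### Sensitivity analysis 4 counts cycle rank only within the study period, so some of its first cycles, and the oocyte yields taken from them, are a woman's second to fifth

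*Protocol*

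**What the plan says.** Table 8 in Protocol Section 9.7.3.9, row 4, reports CLBR for the first three stimulation cycles "by the number of oocytes retrieved in the first cycle (cycle rank expressed as observed in the study period"). Its stated purpose is to explore how oocyte yield in the first cycle relates to CLBR. (Section 9.9.4 and a footnote to Table 1 also say analysis 4 when they mean the laboratory-test analysis, which is row 6. Only row 4 is at issue here.)

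Three other provisions determine who enters:

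- **Analysis set.** CLBR uses Set 2, defined in Section 9.7.1 as "Stimulation cycles with drug of interest and linked FET cycles initiated on or before 31 December 2019". It has no first-ever condition.
- **Prior treatment.** Section 9.2.1 excludes a cycle only for "History of 5 or more IVF/ICSI stimulation cycles prior to the stimulation cycle index date". One to four earlier cycles are allowed.
- **Start dates (Section 9.2.3).** For the HP-hMG comparison: "Denmark, Sweden: 1 January 2010 – 31 December 2020". For the biosimilar comparison: "Denmark: 26 March 2014 – 31 December 2020" and "Sweden: 20 June 2014 – 31 December 2020".

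MC-CLBR and TTLB are treated differently. Set 8 and Sections 9.7.3.3 and 9.7.3.5 confine them to women whose first-ever stimulation cycle fell in the study period.

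**The concern.** A woman already in treatment when the window opens is given rank 1 at her next cycle, whatever her true rank. Her yield in that cycle, possibly after several failures, is then filed as first-cycle yield. Section 9.1.1 itself notes that CLBR falls over the first five cycles, so mixing ranks mixes prognoses.

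At stake is whether Analysis 4 answers its own question. Neither the main nor the stratified analyses relate yield to CLBR, so this is the only planned look at that relation for a primary outcome measure.

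**Working it through.** The protocol gives no figure for this point, so there is none to reproduce.

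**Step 1. The rule applied to one woman.** Suppose her first two lifetime cycles, both with the reference product, were in 2013 and 2015.

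| Comparison | Window opens | Rank of the 2015 cycle | Cycle supplying first-cycle yield |
|---|---|---|---|
| HP-hMG | 1 January 2010 | 2 | 2013 |
| Biosimilars | 26 March or 20 June 2014 | 1 | 2015 |

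The same cycle gets two ranks and two yield strata. This needs no assumption.

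**Step 2. How many cycles are affected.** This depends on continuation and on gaps between cycles, neither of which is in the protocol. Table 2 gives a rough guide to cycles per woman and drug: 53 000/19 000 = 2.79 and 42 000/18 000 = 2.33 (reference product from 2010, Denmark and Sweden); 31 000/14 000 = 2.21 and 22 000/11 000 = 2.00 (reference product from 2014); 5 000/3 000 = 1.67 and 18 000/10 000 = 1.80 (biosimilars). Two sets of simulated treatment histories were used:

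- **Set A:** steady inflow, 15–35% dropout after each failed cycle, mean gap about 7–11 months, CLBR falling from 33% to 22% over cycles 1 to 5.
- **Set B:** first-ever cycle uniform over 1995–2019, one to five cycles with mean 1.7 to 2.79, mean gap 0.5 or 1.0 year, and none or 15% of gaps lasting 2 to 4 years.

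| Rank-1 entries that are not first-ever | Set A | Set B |
|---|---|---|
| Whole window, 2010 start | 5–10% | 3–19% |
| Whole window, 2014 starts | 8–17% | 6–29% |
| Start year | 32–50% (first 12 months) | 25–57% (2010), 29–61% (2014) |

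In Set B, 72–100% of mis-ranked women enter in the start year or the next calendar year, and 98–100% within four calendar years. This concentration assumes that every in-period cycle counts towards rank.

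**Step 3. Effect on rank-1 CLBR.** In Set A the first-year rank-1 CLBR is 30–31% against a true 33%. The implied deficit in mis-ranked cycles is (33 − 31)/0.32 = 6.3 to (33 − 30)/0.50 = 6.0, so about 6 points. The whole-window shift is the mis-ranked share times 6 points:

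- Set A: 0.05 × 6 = 0.3 to 0.17 × 6 = 1.0 point.
- Set B: 0.03 × 6 = 0.2 to 0.29 × 6 = 1.7 points.

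**Step 4. How far register history repairs it.** Section 9.4 dates the Danish IVF register from 1994 and the Swedish one from 2007. Ranking over all register cycles brings mis-ranking to about zero in Denmark. In Sweden, under Set B, it correctly ranks 98–100% of the affected women for the 2014 start, but 70–100% for the 2010 start.

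**The case against.** The best defence is that the rule is openly stated and resembles the overall index date in Section 9.2.3, which is also the first eligible cycle in the study period. On that view it is a debatable definition, used once, in an exploratory sensitivity analysis. This stands as a limit on importance. It does not answer the mismatch with the row's stated aim, which is yield in the first cycle.

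Four stronger readings are tempting, and the protocol does not support them:

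- **That it contradicts a register-wide rank used everywhere else.** Section 9.1.1 does count cycles outside the window for one purpose: "The study will be restricted to the first five stimulation cycles observed in each woman in the IVF registers, regardless if they occurred in the" (and so on). That sentence and exclusion criterion 1 set an eligibility cap, not an analysis rank. TTLB rank, for example, is counted within the given study drug. The firm contrast is with the first-ever restriction for MC-CLBR and TTLB.
- **That it seriously biases the product comparison.** Section 9.9.2 says "the use of rhFSH-alfa biosimilar products has increased gradually, with a relatively larger proportion observed during the latter part of the study period", and Table 1 does not mark calendar year as a propensity-score candidate. A reader might infer that mis-ranked cycles fall mainly in the reference cohort. The shape of uptake is not given, so no split by product can be calculated. Previous failed stimulations and earlier stimulation history are propensity-score candidates, and Analysis 4 reports rates only for the weighted cohorts. Weighting limits the bias between products, but leaves rank and yield strata as labelled.
- **That the problem vanishes after two years.** Women may return years later, including after a live birth. The text also does not say whether in-period cycles with non-study or mixed gonadotropins count towards rank. If they do not, mis-ranking can arise in any year.
- **That the primary results are affected.** The main LBR, CLBR and MC-CLBR analyses do not use this rank.

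**Conclusion.** The concern holds as a badly fixed definition within one sensitivity analysis. As written, rank 1 mixes true first cycles with lifetime cycles 2 to 5, the yield stratum takes on the same mixture, and the two comparisons can rank the same cycle differently. Those statements follow from the text alone.

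The size rests on assumptions: roughly 3–29% of rank-1 entries over the window and 25–61% in the start year. The shift in whole-window rank-1 CLBR is about 1 percentage point or less in most scenarios. It reaches about 1.7 only if the largest Set B share is combined with the 6-point deficit from Set A. The change is worth making because the label is wrong for a known group of women and is easily corrected, not because a main conclusion depends on it.

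**What to change.** In Table 8, row 4, restrict the analysis to women whose first-ever recorded stimulation cycle fell in the study period, as for Set 8. Take the oocyte yield from that cycle, and count ranks 2 and 3 over all later register cycles, whichever gonadotropin was used. The alternative is to keep all women and rank over the whole register.

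State that Swedish history starts in 2007, so some mis-ranking remains for the 2010 start. The restriction copes with this better than re-ranking, because one earlier recorded cycle is enough to remove a woman, whereas correct ranking needs all of them.

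The cost is a short edit and no new data, since prior register cycles are already needed for exclusion criterion 1 and Set 8. The restriction loses some cycles, mostly from the first years of each window. Under the assumptions above, the women lost are the 3–29% now mis-ranked.

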Date of pregnancy test	Continuous	N/A (used to derive outcome variable)		
Pregnancy test result or indicator for pregnancy	Continuous	N/A (used to derive outcome variable)		
Date of ultrasound	Continuous	N/A (used to derive outcome variable)		
Date of pregnancy loss	Continuous	N/A (used to derive outcome variable)		
Other clinical characteristics				
Height/weight or BMI	Continuous	X	X	
Obesity	Categorical	X	X	
Bariatric surgery	Categorical	X	X	
Smoking status*	Numerical	X	X	

Variable	Measurement scale	Baseline characteristic	Candidate variable for PS	Candidate variable for additional adjustment
Type 1 diabetes mellitus	Categorical	X	X	
Type 2 diabetes mellitus	Categorical	X	X	
Antidiabetic drugs	Categorical	X	X	
History of thromboembolic events	Categorical	X	X	
Use of thrombosis prophylaxis	Categorical	X	X	
Porphyria and other relevant conditions [#]	Categorical	X	X	
History of any cancer	Categorical	X	X	
Medical history, fertility-related				
Number of previous failed COS	Categorical	X	X	
History of failed IUI	Categorical	X	X	
History of COS with a study drug	Categorical	X	X	
History of COS with a non-study drug	Categorical	X	X	
Previous delivery with at least one live birth following IVF	Categorical	X	X	
Parity	Categorical	X	X	
OHSS	Categorical	X	X	
Amenorrhea or oligomenorrhea	Categorical	X	X	
PCOS	Categorical	X	X	
Endometriosis	Categorical	X	X	

Variable	Measurement scale	Baseline characteristic	Candidate variable for PS	Candidate variable for additional adjustment
Female infertility diagnosis	Categorical	X	X	
Female factor infertility*	Categorical	X	X	
Male factor infertility*	Categorical	X	X	
Idiopathic factor infertility*	Categorical	X	X	
Medical history, laboratory test results (value at most recent record on or prior to stimulation cycle index date) [†]				
Anti-Müllerian hormone, pmol/L	Continuous	X	X	
FSH, IU/L	Continuous	X	X	
Thyrotropin, mIU/L	Continuous	X	X	
Prolactin, mIU/L	Continuous	X	X	

BMI: body mass index; COS: controlled ovarian stimulation; FET: frozen embryo transfer; FSH: follicle-stimulating hormone; GnRH: gonadotropin-releasing hormone; ICSI: intracytoplasmic sperm injection; IUI: intrauterine insemination; IVF: in vitro fertilization; IU: international unit; L: liter; mIU: milli-international unit; OHSS: ovarian hyperstimulation syndrome; PCOS: polycystic ovarian syndrome; pmol: picomole; PS: propensity score.

Notes:

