9.7.2 Derived and Transformed Data

The data sources included for this study are national healthcare registers that are expected to have a comprehensive coverage and high-quality data. Thus, large amounts of missing data is not expected to be an issue in this study. In case of missing data, a missing data category will be added, and the number of observations and patients with missing data will be reported for each measured variable in the study. The handling of missing data will be described in more detail in the SAP.

The IVF registries may record some of study covariates related to patient characteristics (see Table 1, section 9.3.2), such as smoking status or BMI, only for the patient's first stimulation cycle. Thus, the covariate value from the patient's first stimulation cycle will be used also for the patient's subsequent cycles if the covariate values for the subsequent cycles are missing.

Any study variables and outcomes that are only recorded if an event occurs, such as live birth, are not considered missing. Also, any outcomes relying on the presence of a diagnostic code (i.e. ICD-10), such as OHSS, fit this definition.

Any derived and transformed data needed for conducting the statistical analysis will be described in the SAP.

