6	Adjustment for laboratory test results (Denmark only)	Adjusted analyses will not consider adjustment for relevant laboratory test results.	Completeness of data from the RLRR is uncertain. It is expected that laboratory test results will be available only for a subset of the Danish study population.	An adjusted analysis will be performed among the subset of Danish stimulation cycles or women, depending on the outcome measure, with at least one record of a relevant laboratory test result (see Table 1) available before the stimulation cycle index date (per cycle analyses: LBR, CLBR) or the index date (per woman analysis: MC-CLBR). This adjusted analysis will include relevant	The effect of controlling for relevant predictors of live birth, such as anti-Müllerian hormone levels, will be explored in this analysis. The adjusted analysis of the primary objective and each associated outcome measure (LBR, CLBR, MC-CLBR) will otherwise be repeated as described in 9.7.3.4.

No.	Topic	Main analysis		Sensitivity analysis	
		Method	Justification	Alteration to method	Justification
				laboratory test results as independent variables in the appropriate regression models.	

ICSI: intracytoplasmic sperm injection; IPTW: inverse probability of treatment weighting; IVF: in vitro fertilization; MC-CLBR: multiple-cycle cumulative live birth rate; RLRR: Danish Register of Laboratory Results.

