9.9.4 Unmeasured Confounding

Although a broad range of characteristics will be collected for this study, some relevant predictors of treatment outcomes, such as the antral follicle count and anti-Müllerian hormone levels (60,61),

will not be available from the data collected in Sweden and likely only available for a subset of the Danish study population. Unmeasured confounding cannot be ruled out. However, a sensitivity analysis performed for Denmark will explore the effect of controlling for anti-Müllerian hormone levels and other relevant outcome predictors available from the RLRR (see Analysis 4 in Table 8).

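### Analysis 6, the only planned adjustment for AMH, does not require an AMH value for entry and has no model without AMH in the same subset

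*Protocol*

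**What the plan says.** Table 8 (section 9.7.3.9), Analysis 6, applies to Denmark only. It takes the cycles (for LBR and CLBR) or women (for MC-CLBR) "with at least one record of a relevant laboratory test result (see Table 1) available before the stimulation cycle index date" and adds the laboratory results as independent variables in the outcome regression.

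Table 1 (section 9.3.2) lists the tests: "Anti-Müllerian hormone, pmol/L", FSH, "Thyrotropin, mIU/L" and "Prolactin, mIU/L". It defines each as the "value at most recent record on or prior to stimulation cycle index date", with no maximum age. A note to Table 1 confines laboratory data to a sensitivity analysis because their completeness is uncertain.

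Section 9.7.2 gives the general rule for incomplete covariates: "In case of missing data, a missing data category will be added". It leaves further detail to the SAP.

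Section 9.9.4 names AMH and antral follicle count as predictors that are unavailable in Sweden and likely available only for part of the Danish population. Its response is that a Danish sensitivity analysis will "explore the effect of controlling for anti-Müllerian hormone levels" and other predictors held in the laboratory register.

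Section 9.4.1 says that regions began sending laboratory data gradually from 2013, that coverage is not yet national and that completeness is not reported. The HP-hMG comparison starts on 1 January 2010 (section 9.2.3).

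**The concern.** AMH is a predictor of live birth that the protocol itself names as largely unmeasured, and no other planned analysis adjusts for it. Analysis 4 in Table 8 concerns oocyte yield, which arises after the drug has been chosen and so cannot serve as a check on baseline confounding.

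Two features weaken Analysis 6 for this purpose. First, entry depends on having any one of the four tests, so the subset can include women with no AMH value, for whom nothing is adjusted. An OR that hardly moves could then mean that AMH does not confound, or only that AMH was absent for part of the subset. Second, the subset gets an adjusted model only. If its OR differs from the main Danish OR, the reader cannot tell whether the cause is AMH or the selection of tested women. Either result could be misread as evidence about confounding by ovarian reserve.

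**Working it through.** The protocol gives no figure for this analysis (no AMH share, subset size or expected shift in OR), so there is no figure to reproduce. The check has three steps.

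**1. Who is admitted and how they are handled.** Table 8 requires at least one Table 1 test. Table 1 has four tests. A record of thyrotropin alone meets the rule. Under section 9.7.2 the missing AMH becomes a missing category, so the cycle contributes to the OR unadjusted for AMH.

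**2. How much confounding is left.** Let s be the share of the subset with AMH. If AMH is missing at random, the model combines a part adjusted for AMH (share s) with an unadjusted part (share 1 − s), so approximately

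log OR remaining ≈ (1 − s) × log OR crude (true OR = 1).

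This was checked by simulation: 400,000 cycles, true treatment OR 1.0, standardised AMH, treatment log-odds 0.3 per SD, live-birth log-odds 0.4 per SD with intercept −0.8, and AMH missing at random with a missing indicator. All of these inputs are assumptions. The crude OR was 1.117, so log OR crude = 0.1105.

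| Share with AMH | (1 − s) × 0.1105 | Approximate OR | Simulated OR | Share of log-OR bias left (simulated) |
|---|---|---|---|---|
| 100% | 0 | 1.000 | 0.996 | −4% (simulation error around 0) |
| 90% | 0.011 | 1.011 | 1.008 | 7% |
| 75% | 0.028 | 1.028 | 1.026 | 23% |
| 50% | 0.055 | 1.057 | 1.056 | 49% |
| 25% | 0.083 | 1.086 | 1.086 | 75% |
| 10% | 0.099 | 1.105 | 1.105 | 90% |

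Varying the assumed treatment slope (1,000,000 cycles, outcome intercept −1.1, outcome slope still 0.4):

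| Treatment log-odds per SD | Crude OR | AMH on all | AMH on 50% | AMH on 25% |
|---|---|---|---|---|
| 0.2 | 1.081 | 1.001 | 1.042 | 1.062 |
| 0.4 | 1.165 | 1.003 | 1.084 | 1.124 |

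The size of the OR moves with the assumed slopes. The proportion left, about 1 − s, hardly does.

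An old AMH value has a similar effect. In the 400,000-cycle set-up, with a value for everyone at correlation r with current AMH, the adjusted OR was 1.019 for r = 0.9 (17% of the bias left), 1.058 for r = 0.7 (51%) and 1.087 for r = 0.5 (75%). The correlations are also assumptions.

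**3. What a change in OR can mean.** The main Danish OR for HP-hMG covers cycles from 2010. The subset depends on laboratory transfer that began in 2013, spread by region, and includes private-clinic tests only where samples went to hospital laboratories (section 9.4.1). Table 1 marks calendar year as a baseline characteristic but not as a propensity-score candidate, so a shift in period is not necessarily absorbed by the weights. With one model in the subset,

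change from main OR = effect of restriction + effect of adjustment,

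and the two terms cannot be separated.

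**The case against.** Much of the detail here could properly sit in the SAP. Section 9.7.2 defers missing-data handling, and AMH is listed as continuous, so a missing category would need a coding that the protocol does not give. If the SAP makes the analysis complete-case on AMH, the dilution in step 2 disappears. That stands as a condition on step 2. It does not remove the point: the entry rule is stated in the protocol, and so is the default that keeps women without AMH in the model.

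The stated aim is also wider than AMH, since section 9.9.4 and Table 8 speak of other predictors too. Entry on any test is consistent with that wider aim, but not with reading the result as the effect of controlling for AMH.

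The simulation has one confounder. The actual model is weighted on age, previous failed stimulation, PCOS and infertility diagnosis among others, and FSH, where recorded, would be in the same regression and could recover part of the adjustment. The ORs are therefore illustrative and should not be taken as the bias in this study.

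A reader might also infer three things that the documents do not support:
- **That many admitted women will lack AMH.** The protocol says only that AMH is likely available for a subset of the Danish population. It gives no share among tested women.
- **That the result is formally to be compared with the full Danish cohort.** The protocol says only that the effect will be explored. The full-cohort result is the natural reference because no other is planned.
- **That AMH values from several cycles earlier will affect every primary outcome.** MC-CLBR is limited to women at their first-ever stimulation cycle, so this can arise only for LBR and CLBR.

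**Conclusion.** The point holds. Followed as written, Analysis 6 can include women with no AMH value, and about one minus the share with AMH of the confounding by AMH would remain. This rests on the missing-category default being applied and on AMH being missing at random; the share itself is unknown. Separately, and whatever the missing-data rule, a single adjusted model in the subset cannot distinguish restriction from adjustment.

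The consequence is limited to how a sensitivity analysis in one country can be read. The main analyses are unaffected, and section 9.9.4 already concedes that unmeasured confounding cannot be ruled out. It is still worth correcting, because this is the only evidence on AMH that the study will produce.

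**What to change.** - Require a recorded AMH value for entry to the AMH analysis. FSH, thyrotropin and prolactin may be added in a further step but should not by themselves qualify a woman.
- In that same subset, fit the main IPTW model without AMH and then with AMH, and read the effect of AMH from the difference between the two.
- State in advance a maximum age for the AMH value. Its length is for the sponsor to choose and justify.
- Report AMH availability by study cohort and calendar year.
- Reconcile the text. Table 1 marks laboratory tests as propensity-score candidates while Table 8 puts them in the outcome regression; either route is acceptable, but the two tables should agree. Table 1 allows a value on the index date while Table 8 requires one before it. The note to Table 1 and section 9.9.4 call this Analysis 4, but in Table 8 it is number 6.

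The cost is wording and one extra model per primary outcome and comparison. The subset will be smaller and the estimate less precise, in a sensitivity analysis only.
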